7.13.7.2. Assessment of Psychological Well-Being

Change from baseline to each post-baseline visit at which Psychological Well-Being is assessed will be analyzed using an ANCOVA model. The model for the fixed effects will include terms for the following independent effects: baseline Psychological Well-Being score, treatment.

The Geriatric Depression Scale and the State Trait Anxiety Inventory will also be looked at separately to compare changes between treatments.

7.14. Analyses of Study Drug Exposure and Infusion

Duration of exposure to treatment will be summarized and compared between treatment groups using an ANOVA with treatment as the independent factor.

Duration of exposure (in days) will be derived as follows:

Duration of exposure = Date of study completion/termination – Date of first infusion + 1 day.

Because dosing occurs at study visits, participants who attend all visits and successfully receive complete infusions are automatically compliant with treatment. Any infusion at which 75% or more of the infusate is given will be considered a complete infusion.

Summary statistics will be provided for

- the proportion of participants who received complete infusions at each visit
- duration of complete infusion at each visit, and
- volume of complete infusion at each visit.

The proportion of participants who received complete infusion between treatments will be compared using Fisher's exact test. ANOVA will be used to compare treatment groups for duration of complete infusion, and volume of complete infusion. Treatment will be the independent factor included in the ANOVA.

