Diagnosis and Main Criteria for Inclusion and Exclusions: Subjects will be males and females 65 to 85 years old with preclinical AD, defined as having an MMSE score between 25 and 30, a Logical Memory test, part IIa score between 6 and 18, and a global CDR of 0; and having screening florbetapir PET scan indicating brain amyloid pathology. Subjects will be excluded if they have a screening MRI with results that show >4 ARIA-H or any ARIA-E, have any major or unstable illness, including unstable ischemic cardiovascular disease, or require use of excluded medications.

Number of Planned Subjects: Approximately 1150 (575 solanezumab, 575 placebo).

Dose and Mode of Administration: The study was initiated with solanezumab 400 mg or placebo, administered as an IV infusion once every 4 weeks. Partway through the study, the dose was increased to 1600 mg every 4 weeks. Subjects will receive 400 mg solanezumab or placebo via IV infusion every 4 weeks for at least 2 doses, followed by 800 mg every 4 weeks for at least 2 doses, and then 1600 mg every 4 weeks until the conclusion of the study.

Planned Duration of Treatment:

Screening period: Up to 90 days

Placebo-controlled treatment period: 240 weeks

Open-label treatment period: Up to 204 weeks

Criteria for Evaluation:

Efficacy: PACC, MMSE, ADCS-ADL Prevention Questionnaire, CDR-SB, CFI, C3 (including the C-Path PRO and the Memory Complaint Questionnaire), and the RUI-B.

Disclosure of Amyloid Status: Perception of amyloid imaging as well as impact of disclosure will be assessed using the Views and Perceptions of Amyloid Imaging Questionnaire, the Concerns about Alzheimer's Disease Questionnaire, the Impact of Events Scale, and the Future Time Perspective Scale.

Biomarkers and Imaging: Plasma solanezumab and A β isoforms concentrations and serum anti-solanezumab antibodies (immunogenicity) will be measured from processed blood samples using validated immunoassay and/or mass spectrometry methods. Solanezumab treatment effects will be determined by measuring CSF A β isoforms and tau proteins in those subjects who undergo lumbar puncture and by analyzing amyloid burden on PET scans, as well as volumetric and functional MRI metrics.

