6.1. Summary of Study Design

Study A4 is a multicenter, randomized, double-blind, placebo-controlled, Phase 3 study comparing solanezumab with placebo for 240 weeks in approximately 1150 participants ages 65 to 85 years old with preclinical AD, defined as having evidence of brain amyloid pathology without clinically evident cognitive impairment at screening. Participants who met entry criteria were randomized in a 1:1 ratio (approximately 575 per treatment arm) to solanezumab or placebo once every 4 weeks. Participants were randomized within the site by education – high (13 or more years) or low (12 or less years) and the presence of one or more apolipoprotein E gene (APOE) ϵ 4 alleles (yes, no). The primary hypothesis being tested is that the cognitive decline at the end of the placebo-controlled period will be significantly less for solanezumab than for placebo. Participants completing the placebo-controlled period of the study can opt to participate in the open-label period of the study that will last for up to 204 weeks or until the primary analyses of the placebo-controlled period of the study are completed and reviewed.

At the beginning of the COVID-19 pandemic, a hiatus was implemented to allow participants to pause study activities without missing visits and resume when COVID safety mitigations were in place (for example, vaccines, home infusions, etc.). The hiatus extended the end of the placebo-controlled period for up to 9 months and the placebo-controlled period will be administratively closed in December 2022.

Figure A4.SAP.1 illustrates the study design.

Abbreviation: V = visit.

Figure A4.SAP.1. Illustration of study design for Clinical Protocol A4.

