7.9. Efficacy Analyses

7.9.1. Analysis of Primary Outcome (Placebo-Controlled Period)

7.9.1.1. NCS Analysis of Primary Outcome

The primary objective of this study is to test the hypothesis that intravenous infusion of solanezumab will slow cognitive decline in preclinical AD as compared with placebo.

The original mITT analysis (that is, all participants as randomized to treatment who have a baseline and at least 1 postbaseline measure) for the primary outcome will be retained and conducted at the end of the treatment period, although the dose was increased during the study and dosing and assessments were interrupted due to COVID-19; in other words, the primary analysis will include all data for the solanezumab group as the treatment group versus placebo. As with the original analysis plan, the hypothesis for this analysis will be tested against a two-sided alpha level of .05.

The details of this analysis including the analytic method and model are presented below.

An NCS analysis with 2 degrees of freedom will be used to assess the difference between treatment groups in change from baseline for the PACC score at 240 weeks. The composite score at baseline and each post-baseline visit will be the dependent variable. Time will be treated as a continuous variable with values equal to the years between baseline and follow-up exam dates. We will assume an unstructured covariance structure, where the time values are mapped back to the corresponding visits. The NCS basis expansion will assume an interior knot at the median of observation times, and boundary knots at zero years and the maximum follow-up (Hastie 1992). The fixed effects will include the following terms: (i) NCS basis expansion terms (two terms), (ii) NCS basis expansion terms-by-treatment interaction (two terms), (iii) PACC test version administered, (iv) age, (v) education, (vi) APOE4 Carrier Status (yes/no), and (vii) baseline florbetapir cortical SUVr. The model is constrained to not allow a difference between treatment group means at baseline.

The null hypothesis is that the treatment difference between solanezumab and placebo for the PACC score at 240 weeks is equal to zero. The primary analysis will be carried out in the mITT population that is randomized and has a baseline score and at least 1 post-baseline assessment. If the unstructured covariance structure matrix results in a lack of convergence, the following structures will be used in sequence:

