7.13.1.3. Analyses of TEAEs by Dose

For participants treated with solanezumab, summaries of treatment-emergent adverse events will be displayed with events assigned to the dose (400 mg versus 1600 mg for participants assigned to solanezumab, with events occurring at the 800 mg level assigned to the 1600 mg group, and low dose placebo and high dose placebo for participants assigned to placebo based on the blinded dose level) that the participant was taking at the time of the event. At the first occurrence of a high dose for a participant, all subsequent observations will also be considered as high dose. Events will be reported as frequencies and rates, adjusted for the amount of time until the event for participants who experienced the event or total time on the specified dose for those who did not experience the event. Treatment-emergence will be defined separately for each dose level, with the time period immediately preceding the dose as the baseline period. An adverse event that first appears or worsens in severity subsequent to the dose will be considered treatment-emergent.

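### SAP 7.14 reports time in study as duration of exposure, so the COVID hiatus, missed infusions and time after stopping drug count as exposed time

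*SAP*

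**What the plan says.** SAP 7.14 gives one derivation: "Duration of exposure = Date of study completion/termination", less the date of first infusion, plus one day. It then states that "Duration of exposure to treatment will be summarized and compared between treatment groups using an ANOVA with treatment as the independent factor". The other summaries in 7.14 (complete infusions, infusion duration and infusion volume) are made visit by visit.

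The documents describe three kinds of off-drug time between those two dates:

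- **Hiatus.** SAP 6.1 says that "a hiatus was implemented to allow participants to pause study activities without missing visits" and that "The hiatus extended the end of the placebo-controlled period for up to 9 months". SAP 7.9.1.1 confirms that "dosing and assessments were interrupted due to COVID-19".
- **Missed infusions.** Protocol 9.8 lets participants who miss 3 consecutive infusions, or 10 or more in total, stay in the study with approval.
- **Stopping drug before leaving.** Protocol 8.4.1 treats stopping the product and stopping the study as events that may or may not coincide.

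The by-dose adverse event analysis (SAP 7.13.1.3) adjusts for time to the event in participants who have it, and for "total time on the specified dose for those who did not experience the event". It does not say how that time is derived.

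**The concern.** The formula ends at study exit, not at the last infusion, and subtracts nothing in between. What it measures is time in study, but it is labelled exposure to treatment. Anyone reading the report would take it as time on drug, which for some participants it is not.

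Nothing else in 7.14 would reveal the difference. The per-visit summaries would not show the hiatus, because paused visits were not counted as missed. No number of infusions and no net time on drug is specified. Elsewhere the SAP does adapt to the interruption: 7.9.1.2.4 models cumulative exposure because of the dose increase and the hiatus, and the biomarker sections add continuous-time analyses. Section 7.14 was not adapted.

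At stake are the exposure summary for the safety section and its comparison between arms.

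**Working it through.** The SAP states no exposure figure to reproduce, so the check applies the 7.14 formula to the planned schedule and then to schedules with gaps.

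**Inputs.** Planned length: "Placebo-controlled treatment period: 240 weeks" (Protocol synopsis). Infusions run from Visit 6 to Visit 65, with the last at Week 236 and final assessments four weeks later (Protocol 7.1.3 and Table A4.1). Hiatus: up to 9 months (SAP 6.1). Assumption: 30.44 days per month.

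**No interruption.** 65 − 6 + 1 = 60 infusions; 60 × 28 = 1680 days = 240 weeks. The formula gives 1680 + 1 = 1681 days. Last infusion plus 28 days ends on the same day, so the formula is right here.

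**With gaps.** Overstatement = (formula value − net value) / net value. The net value removes the hiatus, 28 days per missed infusion, or the time beyond 28 days after the last infusion. The lengths below are illustrations, except that 9 months is the documents' maximum.

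| Case (participant stays to Visit 66) | SAP 7.14, days | Net of gaps, days | Overstatement |
|---|---|---|---|
| No gap | 1681 | 1681 | 0% |
| Hiatus 3 months (91 days) | 1772 | 1681 | 5.4% |
| Hiatus 6 months (183 days) | 1864 | 1681 | 10.9% |
| Hiatus 9 months (274 days) | 1955 | 1681 | 16.3% |
| 3 missed infusions, no hiatus | 1681 | 1681 − 84 = 1597 | 5.3% |
| 10 missed infusions, no hiatus | 1681 | 1681 − 280 = 1401 | 20.0% |
| Last infusion Week 232, leaves Week 240 | 1681 | 232 × 7 + 28 + 1 = 1653 | 1.7% |
| Last infusion Week 192, leaves Week 240 | 1681 | 192 × 7 + 28 + 1 = 1373 | 22.4% |

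In weeks, the 9-month case is 39 / 240 = 16.3%, or 279 weeks reported against 240.

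**Average over participants.** Among completers with no other gaps, the mean overstatement is (share who paused) × (hiatus days) / 1681. The documents do not give the share, so only a range can be shown. If 25% paused for 3 months it is 1.4%; 50% for 6 months, 5.4%; 100% for 9 months, 16.3%.

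**The case against.** The best defence is that this is one descriptive variable and little depends on it. Much of that stands. No section names the 7.14 duration as a denominator. The main adverse event comparisons (SAP 7.13.1.1 and 7.13.1.4) are Fisher's exact tests on proportions, which exposure time cannot change. The formula is the same in both arms, so the ANOVA is distorted only if gaps differ by arm, and the documents do not show that they do. If they did differ (Protocol 9.8 gives MRI findings as an example of a medical reason for missed infusions), an ANOVA on time in study would not show it.

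It is also true that the SAP does not ignore gaps: 7.9.1.2.4 models cumulative exposure, and 7.16 lists participants with missed infusions. But the first is a PACC sensitivity analysis and the second a listing. Neither yields a net exposure duration.

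Two stronger readings are tempting and are not supported.

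- **That adverse event rates are understated by 14% (1 − 240/279).** This needs the by-dose rates to use the 7.14 duration and no events to occur during the pause. Section 7.13.1.3 names a different quantity, does not derive it, and uses time to event for those who have the event. Treatment emergence in 7.13.1.1 has no off-drug cut-off, and 7.13.1.3 assigns everything after the first high dose to the high dose. Events during a pause therefore stay in the numerator. If they occur at the same rate on and off drug, keeping the pause in the denominator causes no understatement.
- **That the error is always larger for someone who stops infusions but stays in the study.** It depends on the time off drug. The Week 232 case has 28 excess days against 274 for the full hiatus. Protocol 8.4.1 also encourages an early termination visit when drug is stopped, and no figure is given for long off-drug follow-up.

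**Conclusion.** The point holds as a mislabelled and, for some participants, overstated safety quantity. As written, SAP 7.14 counts the hiatus, missed infusions and time after stopping drug as exposure to treatment. For a completer with the full hiatus and no other gap, the overstatement is about 16%. It is zero for an uninterrupted completer. The trial average is unknown and rests entirely on how many paused and for how long.

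The effect is confined to the exposure summary and its ANOVA. The primary PACC analysis, the cumulative-exposure model and the Fisher's exact adverse event comparisons are untouched. Whether the by-dose rates in 7.13.1.3 are affected cannot be settled, because their time on dose is not derived.

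One further ambiguity is that the end date in 7.14 is not tied to the placebo-controlled period, whereas SAP 7.7 uses the completion date of the double-blind period. Read literally, open-label time could be counted too.

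**What to change.** 1. In SAP 7.14, define exposure for the placebo-controlled period as the last placebo-controlled infusion date + 28 days − the first infusion date. Cap it at the end of that period, or at the first open-label infusion. Subtract the hiatus and the intervals in which scheduled infusions were not given. Say that variation within the ±10-day visit window is not a gap, and whether the SAP's extra day is kept.
2. Keep the present quantity and report it as time in study, with its end date tied to a named period.
3. In SAP 7.13.1.3, state how time on each dose is derived, and treat paused time the same way on both sides of the rate: paused time and the events in it are both included or both excluded. Removing the pause from the denominator alone would push the rates up.

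The cost is SAP wording and one derivation. It uses infusion dates, and Protocol 9.8 already requires missed and incomplete infusions to be recorded on the case report form, so no new data are needed. The reported exposure will be shorter for participants with gaps.

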7.15. Subgroup Analyses

To assess the effects of various demographic and baseline characteristics on treatment outcome, subgroup analyses for the primary endpoint, PACC, will be performed based on the following variables:

- Gender: Male/Female
- Age: ≥ 65 years and < 75 years, ≥ 75 years and < 85 years
- Race: Dichotomized based on distribution of race at baseline.
- APOE4 Carrier Status: Carrier defined as $\epsilon 2/\epsilon 4$, $\epsilon 3/\epsilon 4$, or $\epsilon 4/\epsilon 4$ genotype; Non-Carrier defined as all other genotypes.
- APOE4 Genotype: $\epsilon 2/\epsilon 4$, $\epsilon 3/\epsilon 4$, $\epsilon 4/\epsilon 4$, No $\epsilon 4$
- Family History of AD: Yes/No
- Reason for Discontinuation: Categories as defined by the subject disposition case report form. Due to sparseness within certain categories, categories may be collapsed after seeing the actual distributions.

The primary outcome measures will be modeled using an NCS approach. This general model will include effects for (i) NCS basis expansion terms, (ii) subgroup (iii) NCS basis expansion terms-by-treatment-by-subgroup interaction, (iv) PACC test version administered, (v) age, (vi) education, (vii) APOE4 Carrier Status (yes/no), and (viii) baseline florbetapir cortical SUVr. This model will constrain the baseline treatment group means to be the same within subgroup levels, but allow different baseline means for the subgroups. Redundant terms will be dropped from the model in those cases in which the subgroup of interest is overlapping with this general model. The interaction will be tested by likelihood ratio test comparing the full model to the reduced model without any subgroup interaction effects.

To evaluate dose effect on the primary outcome measure, marginal structural models, inverse probability of treatment weighting (MSM, IPTW) methodology will be used (Lipkovich et al, 2008). Dose profiles for mean changes from baseline will be evaluated using weighted MSM with a repeated measures model. To adjust for selection bias due to non-random dose assignment and dropouts, participant-specific time-dependent weights will be determined as products of (i) stable weights based on inverse probability of receiving the sequence of dose assignments that was actually received by a participant up to given time multiplied by (ii) stable weights based on inverse probability of participant remaining on treatment by that time.

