7.1.2. Screening Phase (Visits 1 to 5)

The entire screening period spans the time from Visit 1 to Visit 5. Study assessments are shown in the Study Schedule ([Attachment 1](#)).

Up to 90 days are permitted to allow for completion of all screening procedures, assessments, A β status disclosure, and evaluation of results from laboratory tests, ECGs, PET imaging, MRI, and optional lumbar puncture (LP). A central read of the MRI should be completed before an LP is performed.

The subject can only proceed to baseline (Visit 6) once all screening procedures as described in the Study Schedule ([Attachment 1](#)) are completed and the investigator or qualified designee and clinical monitor have confirmed that the subject is eligible to be randomized.

Current or planned use of concomitant medications, the effects of vacations or absences on protocol compliance, and general compliance with the protocol will be discussed during the screening phase. Subjects who do not meet all inclusion criteria or who meet any exclusion criteria will not be allowed to participate in the study.

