7.2. Discussion of Design and Control

Study Population. As AD is thought to represent a continuum of disease, discrete stages of AD will of necessity need to be operationally defined. Entry criteria were chosen to maximize selection of individuals who are still considered clinically normal but who may be at high risk of subsequent cognitive decline and the eventual onset of clinical signs and symptoms diagnostic of prodromal or mild AD. Cut-points for screening memory tests will exclude individuals who are

performing >0.5 standard deviation (SD) above age- and education-adjusted normative means, as these individuals may be better able to compensate for imminent cognitive decline over the course of the study. Instead, the study will enroll people who have memory performance down to 1.0 SD below education-adjusted normative means, which overlaps the cognitive performance range of early MCI without meeting the definition for MCI (since CDR must be 0). Recent evidence suggests that people with evidence of amyloid pathology are more likely to perform in the bottom of the “normal range” on sensitive neuropsychological tests and have a higher risk of cognitive decline and progression to MCI and AD dementia (Doraiswamy et al. 2012; Knopman et al. 2012; Sperling et al. 2013; Villemagne et al. 2013). Furthermore, subjects are required to be ages 65 to 85 at the time of screening, to maximize the likelihood of identifying subjects that will meet the preclinical AD amyloid pathology inclusion criteria, as research in the field suggests that incidence/prevalence of amyloid pathology is highest in this group compared to those under age 65. Measures will be in place to ensure sufficient enrollment of individuals at the higher end of this age range and to enroll under-represented minority populations.

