8.1. Inclusion Criteria

A subject is eligible to be included in the study only if he or she meets all of the following criteria:

- [1] Male or female ages 65 to 85 years old.
- [2] Has an MMSE score at screening of 25 to 30.
- [3] Has a global CDR score at screening of 0.
- [4] Has a Logical Memory II score at screening of 6 to 18.
- [5] Has a florbetapir PET scan that shows evidence of brain amyloid pathology at Visit 2.
- [6] In general, permitted medications should be stable for 6 weeks prior to baseline (Visit 6). Changes to medications that, in the opinion of the investigator, are not likely to impact baseline visit assessments are permissible.
- [7] Has a study partner that is willing to participate as a source of information and has at least weekly contact with the subject (contact can be in-person, via telephone or electronic communication). The study partner must have sufficient contact such that the investigator feels the study partner can provide meaningful information about the subject's daily function.

- [8] In the investigator's opinion, is both willing and able to participate in all required procedures for the duration of the study (at least 240 weeks), including adequate literacy in English, Spanish, or Japanese, and adequate vision and hearing to complete the required psychometric tests.

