7.13.1.2. Subgroup Analyses of TEAEs

Subgroup analyses of TEAEs will also be done. The subgroups will include age at baseline (≥ 65 and < 75 years, ≥ 75 and < 85 years), gender, and race (dichotomized based on distribution of race at baseline). For each subgroup variable, a Breslow-Day test of homogeneity of odds-ratios between treatment groups will be performed on the incidence of each TEAE.

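### The SAP's two age subgroups stop below 85 while entry is allowed up to 85, so participants aged 85 belong to no age stratum in the PACC and adverse-event subgroup analyses

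*SAP*

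**What the plan says.** Eligibility. Inclusion criterion [1] in Protocol 8.1 reads "Male or female ages 65 to 85 years old". Protocol 7.2 fixes the time at which this is judged: "subjects are required to be ages 65 to 85 at the time of screening". SAP 6.1 repeats the range: "approximately 1150 participants ages 65 to 85 years old with preclinical AD". Screening can be long, since Protocol 7.1.2 states "Up to 90 days are permitted to allow for completion of all screening procedures".

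Age subgroups. For the PACC, SAP 7.15 lists "Age: ≥ 65 years and < 75 years, ≥ 75 years and < 85 years". For treatment-emergent adverse events, SAP 7.13.1.2 states "The subgroups will include age at baseline (≥ 65 and < 75 years, ≥ 75 and < 85 years), gender, and race". The adverse-event section specifies age at baseline. The age bullet in SAP 7.15 does not name the time point; its lead-in refers only to demographic and baseline characteristics in general.

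Neither SAP section has a category for age 85 or above, or a rule for someone who fits no category. Protocol 11.2.14 announces subgroup analyses without giving cut-points, so nothing there overrides the SAP.

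**The concern.** Subgroup levels used to test whether the treatment effect differs by age should cover everyone in the analysis population. Other factors in SAP 7.15 are set up that way: gender has two levels, race is dichotomised, and APOE4 non-carriers are defined as everyone not a carrier. Age has a closed upper limit that excludes an eligible age.

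Three things are at stake.

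- The participants omitted are not a random subset. All come from the top of the age range, so the older-stratum PACC estimates and event rates would describe ages 75 to 84 only.
- Age-stratum counts would not reconcile with the mITT total (PACC) or the safety total (adverse events), although SAP 7.1 makes those populations the default.
- The text does not determine a single analysis. A programmer who codes both limits literally and one who codes under 75 versus all others get different data sets. If the gap is noticed only after unblinding, the choice between them becomes a post hoc one.

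**Working it through.** The plan states no figure to reproduce here. The check is one of set membership, followed by a count under a stated assumption.

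**Step 1. Compare the ranges.**

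| Item | Range | Time point | Source |
|---|---|---|---|
| Eligible ages | 65 to 85 | Screening | Protocol 8.1 and 7.2; range repeated in SAP 6.1 |
| PACC strata | [65, 75) and [75, 85) | Not named in the bullet | SAP 7.15 |
| Adverse-event strata | [65, 75) and [75, 85) | Baseline | SAP 7.13.1.2 |

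**Step 2. Assign each eligible age in completed years.** There are 85 − 65 + 1 = 21 ages.

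- 65 to 74: 10 ages, all in the younger stratum.
- 75 to 84: 10 ages, all in the older stratum.
- 85: fails < 75 and fails < 85, so it is in neither.

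That is 20 ages placed once each and one age not placed.

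**Step 3. Try the narrowest reading of eligibility.** Suppose the entry range ended at the 85th birthday. Someone aged 84 at screening can still turn 85 during the up to 90 days before baseline. Under SAP 7.13.1.2, which uses age at baseline, that person is unplaced. The narrow reading shrinks the gap without closing it.

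**Step 4. Follow an unplaced participant through the two analyses.**

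- *PACC (SAP 7.15).* The model has a subgroup main effect and an interaction of spline terms, treatment and subgroup. The likelihood ratio test compares it with a model that drops only the subgroup interactions. A participant with no subgroup value can enter neither model, and so is absent from the test and from both stratum estimates.
- *Adverse events (SAP 7.13.1.2).* The Breslow-Day test is built from one two-by-two table per stratum. A participant in no stratum is in no table.

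**Step 5. Size.** The documents give no age distribution. Let p be the proportion aged 85 or older at baseline, with N = 1150 (SAP 6.1). Number unplaced = N × p.

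| Assumed p | N × p | Participants, both arms |
|---|---|---|
| 0.5% | 1150 × 0.005 = 5.75 | about 6 |
| 1% | 1150 × 0.01 = 11.5 | about 12 |
| 2% | 1150 × 0.02 = 23 | 23 |

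With 1:1 randomisation, the range is roughly 3 to 12 per arm.

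**Step 6. Test the repair.** With strata [65, 75) and ≥ 75, each of the 21 eligible ages falls in exactly one stratum. Anyone who turns 85 or 86 between screening and baseline is also placed. Writing the upper limit as ≤ 85 would place all 21 ages too, but would miss a person who turns 86 before baseline.

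**The case against.** The strongest reply is that this is a boundary slip with little reach, and most of that stands. The primary model in SAP 7.9.1.1 takes age as a covariate with no cut-off and uses the whole mITT population. The main comparisons of adverse events, serious events and discontinuations (SAP 7.13.1.1) and the event clusters (SAP 7.13.1.4) do not use age strata. SAP 7.4 makes everything other than the primary PACC analysis secondary to it. No primary estimate, significance level or power figure changes.

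It is also fair to say that exclusion is an inference. The SAP does not instruct anyone to drop 85-year-olds; it simply fails to place them. The likely intention was ≤ 85 or ≥ 75, and mismatched totals might expose the slip when output is checked. That makes the problem easier to catch, but the text remains wrong. The same limit appears in both sections, so comparing one with the other would not reveal it.

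A reader might infer more than the documents support:

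- *That about 55 participants are lost.* This comes from 1150 / 21 = 54.8, which assumes equal enrolment at every age. Nothing in the documents supports a uniform age distribution.
- *That the older half of the trial is misdescribed.* No passage says what share of participants is 75 or older.
- *That the protocol set out to recruit the very people omitted.* Protocol 7.2 says "Measures will be in place to ensure sufficient enrollment of individuals at the higher end of this age range". Ages 75 to 84 also fit that description, and they are classified.
- *That both sections use age at baseline.* Only SAP 7.13.1.2 says so.

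**Conclusion.** The point holds as a definite but limited error. The SAP's age strata do not cover the eligible age range, and no other passage closes the gap. Participants aged 85, including those who reach 85 between screening and baseline, have no stratum in the PACC or adverse-event age analyses.

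The size is unknown. The figure of about 6 to 23 participants rests entirely on the assumed 0.5% to 2%, and the true count could be smaller or larger. No effect on a subgroup estimate or test can be calculated from the documents. The conclusion assumes that the strata are applied as written.

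The consequence is confined to the age-subgroup results and the reconciliation of their totals. It would be wrong to read this as a threat to the primary result or to the overall safety comparisons.

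**What to change.** In SAP 7.15 and SAP 7.13.1.2, replace the older stratum with ≥ 75 years and no upper limit. While editing SAP 7.15, state that age means age at baseline, so that the two sections agree.

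The cost is a wording change in two places. It needs no new data and leaves the primary analysis and the significance level as they are. Because the protocol sets no age cut-points, no protocol amendment appears to be needed under Protocol 11.2.1. The change is best made before any unblinded subgroup output is produced. If that point has passed, the clinical study report should state how participants aged 85 or older were assigned and when that was decided.
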